9.6.1.3 Assessments and documentation of adverse events

The investigator has to record on the respective CRF pages all AEs occurring in the period between the signing of the informed consent and the end of the follow-up phase; after the end of the follow-up phase there is no requirement to actively collect AEs including deaths. The type of information that should be assessed and recorded by the investigator for each AE is listed in Section [9.6.1.2](#).

“Death” should not be recorded as an AE on the AE page. Instead, “death” is the outcome of underlying AE(s).

For all SAEs, the sponsor has to carry out a separate assessment for expectedness, seriousness, and causal relationship to study procedure.

Investigator responsibility

Investigators must record and document all AEs on the AE CRF.

- If the AE is an SAE or MDR (including device or procedure-related AEs / effects and deaths), it must be reported immediately (within 24 hours) to the relevant institutional review board (IRB) / Ethics Committee (per local requirements) and to the sponsor by the investigator and recorded on the CRF. The investigator will send to the sponsor,

all appropriate paper work (discharge summaries, office notes, etc.) that might be pertinent. Reports relating to the subjects' subsequent medical course must be submitted to the sponsor until the event has subsided or, in case of permanent impairment, until the event stabilizes and the overall clinical outcome has been ascertained.

- If the AE is also a UADE, it must be reported to the sponsor and the reviewing IRB / Ethics Committee (per local requirements) as soon as possible but no longer than 3 working days after becoming aware of the event. The investigator will send to the sponsor all appropriate paperwork (discharge summaries, office notes, etc.) that might be pertinent. Reports related to the subject's subsequent medical course must be submitted to the sponsor until the event has subsided or, in case of permanent impairment, until the event stabilizes and the overall clinical outcome has been ascertained.

Sponsor responsibility

- The Sponsor will be responsible for categorizing SAEs / serious adverse device effect (SADEs) in terms of expectedness, seriousness, and causal relationship to the Essure device when all necessary data are available.

MDR / SADE Reporting – Because this study involves using a commercially approved device in accordance with labeling, the device is subject to MDR regulations, 21 CFR 803 / MEDDEV 2.7.3. The sponsor will review all AEs and follow the guidelines of the MDR regulations for those events that can be attributed solely to the insert placement procedure and device wearing and report based on local regulations.

9.6.1.4 Reporting of serious adverse events

Section modified by Amendment 2 ([Modification 24](#)).

The definition of SAEs is given in Section [9.6.1.1](#). Each SAE must be followed up until resolution or stabilization by submission of updated reports to the designated recipient.

Investigator's notification of the sponsor

All investigators will be thoroughly instructed and trained on all relevant aspects of the investigator's reporting obligations for SAEs and SADEs / incidents. This information, including all relevant contact details, is summarized in the investigator site file (ISF). This information will be updated as needed.

All SAEs / MDRs occurring during the observation period defined in Section [9](#) must immediately (within 24 hours of the investigator's awareness) be reported to the sponsor's designated recipient. A SAE form must also be completed within 24 hours of the investigator awareness and forwarded to the sponsor's designated recipient.

Each SAE / MDR must be followed up until resolution or stabilization by submission of updated reports to the designated recipient. Any SAE / MDR occurring after the protocol-defined observation period will be processed by the sponsor's designated recipient according to all applicable regulations.

In addition, device failures, malfunctions or MDRs must be reported to sponsor's designated recipient within 24 hours via fax or email. In case of a device failure, malfunction, or SADE related to the device, the device must be returned to the sponsor's product surveillance department for analysis.

Ectopic pregnancies and spontaneous abortions are always to be considered SAEs and reported as such to the sponsor's designated recipient within 24 hours.

Notification of the independent ethics committee (IECs) / IRBs

Notification of the IECs / IRBs about all relevant events (e.g., SAEs / MDRs, UADEs, device failures, device malfunctions) in the study will be performed by the sponsor and / or by the investigator according to all applicable regulations.

Notification of the authorities

The processing and reporting of all relevant events (e.g., SAEs / MDRs, UADEs, device failures, device malfunctions) to the authorities will be done by the sponsor according to all applicable regulations.

Sponsor's notification of the investigational site

The sponsor will inform all investigational sites about reported relevant events (e.g., SAEs / MDRs, ADEs, UADEs, device failures, device malfunctions) according to all applicable regulations.

9.6.1.5 Expected adverse events

For this medical device study, the applicable reference document is the most current version of the US IFU.

The expectedness of AEs will be determined by the sponsor according to the applicable reference document and according to all local regulations.

9.6.1.6 Device removal and surgical pathology

Section modified by Amendment 1 (Section 16.1) and Amendment 2 ([Modification 5](#)).

Each time a surgical procedure is performed (Essure or laparoscopic tubal ligation), additional information will be collected about the circumstances surrounding the surgery (e.g., date of placement, reason for removal, procedure details, any energy sources used, vasoconstrictive agent used, imaging to assist with confirming the location of the insert, and the location and status of the device removed). Subjects who have had surgical intervention or their device removed will continue to be followed for the collection of safety and laboratory data.

Prior to any planned surgical removal of an Essure insert, salpingectomy, or hysterectomy, the investigator must contact the sponsor in order to arrange for handling of the pathology specimen. This is important as improper handling of specimens may preclude the performance of metallurgic analyses.

Whenever possible, and if clinically and surgically appropriate, if the decision is to remove the fallopian tube, this should be done with the Essure insert or sterilization device, if

applicable (e.g., Falope ring, Filshie clip) in situ. In the case of Essure, this can be accomplished by making a circumferential incision around the proximal tube near the cornua, then pulling the proximal most portion of the insert from the cornua (while the remainder of the insert remains in the tube that is removed), or with a cornual resection. Physician judgment as to the appropriate procedure for the subject will take precedence over obtaining a pathology specimen. If a hysterectomy is clinically and surgically appropriate, it should be performed with the tubes attached to the uterus, if possible.

In the Essure group, ideal specimens will have the Essure insert in situ as this will provide the most complete information; however, all tubes, regardless of presence of the insert, should be submitted for examination. In addition, all inserts, regardless of whether they are in situ or previously removed, should be submitted. Processing for tubes with and without inserts in situ will need to be slightly different.

In the laparoscopic sterilization group, ideal specimens will be fallopian tubes with sterilization devices in situ, if applicable (e.g., Falope ring, Filshie clip); however, all tubes should be submitted regardless of presence of a previously applied sterilization device.

After removal of the specimen, the pathologist should provide a gross description of the specimen and obtain photographs of both the anterior and posterior aspects of the specimen. If the specimen consists of the fallopian tube only, the proximal portion of the tube, the portion of the tube containing the insert / device / or cauterized section, together with a 2 cm section immediately distal to the insert / device or cauterized section, should be removed (as one specimen) and placed in formalin. If the specimen also has the uterine cornua attached to the tube, the cornua should also be included as part of the specimen. If the tube is attached to the uterus, the cornua should be removed from the uterus along with the portions of the tube noted above. In the case of Essure, if the insert has already been removed from the tube, the surgeon should tie a single non-metallic suture around the tube indicating the proximal location of where the insert was located in the tube and a double non-metallic suture around the tube indicating the distal location of where the insert was located in the tube (if applicable / possible). This is necessary for subsequent metallurgic testing in the event the insert is missing from the tube. The specimen will then be placed in formalin and sent to a central gynecologic pathology laboratory for processing. Any explanted Essure inserts should also be placed in formalin and sent.

Once at the central processing location, in the case of Essure, the specimen will be divided into 3 sections: the first section will be kept within the gynecologic pathology laboratory for additional processing, the second section will be sent to a specialized laboratory for methacrylate embedding, and a third section will be sent to a specialized laboratory for metallurgic testing. If the insert has been removed from the tube, an x-ray of the tube will be necessary to ensure no fragment of insert remains in the tube. If there are no metallic components in the tube, methacrylate embedding will be unnecessary.

For the basic gynecology histology section, in a portion of the tube containing the Essure insert, the tissue will be carefully micro-dissected free from the insert and then embedded in paraffin and sectioned prior to histologic examination. Sectioning will include areas of the tube containing the insert as well as a section of the tube at least 1 to 1.5 cm distal to the insert as an internal control. A second portion of the tube containing the Essure insert will be

sent to a specialized pathology laboratory for methacrylate embedding and sectioning. This will allow for subsequent histologic examination of the specimen with the insert in situ. Sections will be made both of the tube with the insert in situ as well as a portion of the tube distal to the insert for comparison.

A standardized scoring protocol based on ISO 10-993, part 6 criteria will be used to assess inflammatory response. The H&E, Movat's pentachrome, and CD68 immunostaining will be performed on both methacrylate and paraffin embedded specimens. If on stained slides there appears to be a moderate or extensive inflammatory reaction, immunohistochemical staining for additional markers will be performed. These will be performed on both methacrylate and paraffin embedded specimens; however, some stains may not be possible on methacrylate embedded specimens.

Due to the number of expected pathological specimens, evaluation will be qualitative. Comparisons can be made between the area of the tube containing the insert versus the area of the tube distal to the insert. Any additional qualitative comparisons will be entirely dependent on availability of specimens in each of the potential comparator groups. If sufficient samples exist, it may be possible to compare histology findings in women who have removals due to pain and / or other AEs to women who have their tubes removed for other unrelated issues. In addition, if available, tubal histology in the Essure group can be qualitatively compared to tubal histology in the laparoscopic sterilization group.

The third portion of the tube will be sent to a specialized laboratory for metallurgic testing to determine nickel and titanium content / presence in the adjacent tissue both in the tissue immediately adjacent to the insert as well as in tissue distal to the insert. This will be accomplished through inductively coupled plasma mass spectrometry (ICPMS). Information derived from ICPMS will be correlated with blood levels of nickel and titanium taken from the subject at various times both pre- and post-implant removal. Tissue nickel and titanium concentrations will be compared in the section of tube containing the insert versus the section of tube distal to the insert. Additional qualitative comparisons will be entirely dependent on the availability of specimens. If appropriate specimens are available, tissue nickel and titanium concentrations in women with complaint of pain or hypersensitivity / allergic reactions can be compared to tissue nickel and titanium concentrations in women who have their tubes removed for other (non-AE associated) reasons. In the case of tubes where the insert has been previously removed, surgeons will be asked to indicate the location of the insert by tying non-metallic suture at each end, as described above. In addition to assessing metal concentrations in tissue, metallurgic examination will also look at Essure inserts. The ideal insert is one that is micro-dissected in the laboratory as this will have the least deformation / artifact. The inserts will be examined to look for pitting and loss of material. In cases of inserts already removed from the tube, examination will be restricted to areas not exposed to deformation.

In the case of laparoscopic tubal sterilization, specimens will be embedded in paraffin prior to sectioning for histology and stained and examined in the same way as noted above for the Essure group. If a device (e.g., Falope ring, Filshie clip) is attached to the tube, it will be carefully removed prior to processing. There will be no need for methacrylate embedding or metallurgic testing in the case of laparoscopic sterilization.

9.6.2 Pregnancies

Section modified due to Amendment 2 (Modification 21).

If a subject becomes pregnant (i.e., an unintended pregnancy) at any time following the visit in which she is told to rely on Essure, the pregnancy will be counted as a device failure. Following the resolution of the pregnancy, subject will be asked to undergo an HSG. Subject will also be counseled that she can no longer rely on Essure for contraception.

If a subject becomes pregnant (i.e., an unintended pregnancy) at any time following her sterilization procedure, the pregnancy will be counted as a sterilization failure. The pregnancy will be followed to resolution. The subject will then be managed as per local standard of care, at the discretion of the treating physician.

The investigator must report to the sponsor any pregnancy occurring in a study subject during the subject's participation in this study (i.e., after signing of the informed consent). The report should be submitted within the same timelines as an SAE, although a pregnancy per se is not considered an SAE. For a study subject, the outcome of the pregnancy should be followed up carefully and the outcome of the pregnancy for both the mother and the child are to be reported using the Pregnancy Form provided.

9.6.3 Further safety

9.6.3.1 Laboratory evaluations

Section modified by Amendment 2 (Modification 4).

Several different laboratory assays will be conducted on whole blood or serum/plasma samples throughout the study. A summary of the samples to be collected and assays to be performed include:

- HLA typing (obtained from lymphocytes)
Certain HLA types are associated with specific autoimmune diseases. In addition, preliminary research indicates that some HLA types may be related to an increased

risk of nickel hypersensitivity reactions. A whole blood sample will be collected at baseline and will be used to characterize nickel hypersensitivity and to evaluate HLA in subjects diagnosed with an autoimmune disease.

- To characterize nickel hypersensitivity, an HLA panel, including HLA-antigen D Related (HLA-DR) subunits B1, B3, B4, and B5 (which are related to potential reactions to nickel) will be run on the baseline sample for all subjects. Any remaining specimen will be stored frozen for future additional HLA typing, only for subjects diagnosed with an autoimmune disease.
 - To characterize specific autoimmune diseases in subjects with an autoimmune disease diagnosis, the HLA type specific to that autoimmune disease will be run. The HLA type to be evaluated will be selected in consultation with an immunologist and / or rheumatologist and will depend on the specific autoimmune disease diagnosed. For each HLA type that is evaluated, a randomly selected control group of subjects without the specific autoimmune disease will be identified, and the HLA type run in the index case will be run as a control sample. The size of this control group will depend on the frequency of the specific HLA type in the population.
- Nickel lymphocyte proliferation test (NiLPT)
The NiLPT is a measure of sensitization to nickel. A whole blood sample will be collected and sent by the site to a single specialty laboratory, and must be received in the laboratory within 24 hours. This test will be drawn and run at baseline and at 12 months in all subjects. In addition, if at any point in the study a subject develops symptoms that could be due to hypersensitivity or autoimmune process, including pelvic pain, an unscheduled NiLPT sample will be drawn. The continuous score and the positive / negative score (based on a cutoff for negative response of Stimulation Index (SI) < 5.7) will be recorded.
- Chromium lymphocyte proliferation test (LPT)
The LPT is a measure of sensitization to chromium. This test requires whole blood and must be received in the laboratory within 24 hours. Due to the very low positivity rate for this test, it will only be drawn if a subject develops symptoms that could be due to hypersensitivity or autoimmune process, including pelvic pain.
- Serum nickel level
This test will be drawn and run at baseline, at 12 months, and at 60 months in all subjects. In addition, if at any point in the study a subject develops symptoms that could be due to hypersensitivity or autoimmune process, including pelvic pain, an unscheduled serum nickel level will be re-drawn. Gadolinium and iodine-based contrast material are known to interfere with trace metal analysis; therefore, specimen collection for serum/plasma nickel and titanium should be deferred until 96 hours following administration of gadolinium or iodine contrast media.
- Serum titanium level
This test will be drawn and run at baseline and at 1 year in all subjects. In addition, if at any point in the study a subject develops symptoms that could be due to hypersensitivity or autoimmune process, including pelvic pain; an unscheduled serum titanium level will be re-drawn. Gadolinium and iodine-based contrast material are

known to interfere with trace metal analysis; therefore, specimen collection for serum/plasma nickel and titanium should be deferred until 96 hours following administration of gadolinium or iodine contrast media.

- Serum

Serum will be collected at baseline and at 1 year on all subjects. This serum will be frozen. For all subjects, this serum will be used to run a baseline and one-year inflammatory cytokine panel (to include IFN- γ , IL-10, IL-4, TGF- β , TNF- α , p40 subunit (IL-12, IL-23), p35 subunit (IL-12, IL35), and IL-17). Any remaining serum will be frozen. It will be used if a subject develops an autoimmune disease. In these cases, the serum can be used to obtain baseline levels for the particular diagnosed autoimmune condition (e.g. a Rheumatoid Factor if subject is diagnosed with rheumatoid arthritis; thyroid peroxidase antibody if subject is diagnosed with autoimmune thyroid disease. Given the number of potential diseases, it is not possible to establish a baseline for every potential autoimmune disease). If any serum remains after running these tests, it will remain frozen.

At 60 months, additional serum will be drawn. This will be sent for a repeat inflammatory cytokine panel.

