9.2.2.11 Sixty months post-procedure (-4 wk, +1 wk) (End of Study)

Section added by Amendment 2 (Modification 3, Modification 4, Modification 17, Modification 18).

A subject for whom the 60-month visit is complete is considered a completed subject. Once completed, no additional study-related subject data will be collected. The End of Study form should be filled out at subject's 60-month visit.

- AE assessment, including but not limited to the following AEs of interest:
 - Infection, uterine or tubal perforation, device migration, device expulsion;
 - Allergic / hypersensitivity reactions, development of autoimmune-like symptoms.

- Device events (see Section 9.6.1.1 for details);
- Concomitant medications;
- Weight and vital signs;
- Type of alternate contraception (if applicable);
- Pregnancy including pregnancy outcomes;
- Gynecological procedures such as endometrial ablation, hysterectomy, salpingectomy, oophorectomy, operative hysteroscopy, any other relevant gynecological events, and complications and outcomes including those associated with device removal (e.g., symptom resolution);
- Any new exposure to metals (e.g., piercings, orthodontics);
- If indicated for potential hypersensitivity reaction / pain AEs / allergy / autoimmune disorder:
 - Whole blood samples for NiLPT and chromium LPT;
 - Serum or plasma samples for nickel and titanium levels. Gadolinium and iodine-based contrast material are known to interfere with trace metal analysis; therefore, specimen collection for serum/plasma nickel and titanium should be deferred until 96 hours following administration of gadolinium or iodine contrast media;
- If indicated for potential autoimmune disorder:
 - Testing of previously frozen serum samples for autoimmune markers (as indicated, if sufficient serum is available). Any remaining serum will remain frozen.
 - Appropriate HLA panel from previously obtained baseline samples (or redraw if insufficient sample remains).
- Serum for inflammatory cytokine panel (see Section 9.6.3.1)
- PRO assessment(s):
 - Screening question for lower abdominal / pelvic pain, and, if positive:
 - PROMIS (3a);
 - PROMIS (8a).
 - AMSS and 2 intermenstrual bleeding questions;
 - SF-36;
 - Completion of Supplemental PRO Questionnaires;
 - Completion of Social Media Questionnaire.

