- Levels of inflammatory markers and HLA type in subjects with Essure and adjudicated hypersensitivity reactions can be compared to corresponding findings in subjects with Essure without hypersensitivity reactions as well as to laboratory results in laparoscopic tubal ligation subjects (with and without adjudicated hypersensitivity reactions). Serum cytokine values will be classified as below the normal range, within the normal range, or above the normal range, as appropriate. These values will be used to provide descriptive summaries of change of categories between baseline and

Year 1 and between baseline and Year 5. For these analyses the safety population will be used to present data by treatment groups and by symptomatic/asymptomatic subjects. Secondary analyses can also be performed in subjects who report positively to events on the Supplementary PRO tools (e.g. fatigue, headache) versus those who do not. These comparisons will not rely on device removal.

- Serum or plasma nickel and titanium levels in subjects with Essure and adjudicated hypersensitivity reactions can be compared to serum or plasma nickel and titanium levels in subjects with Essure without hypersensitivity reactions as well as to serum or plasma nickel and titanium levels in laparoscopic tubal ligation subjects (with and without adjudicated hypersensitivity reactions). Secondary analyses can also be performed in subjects who report positively to events on the Supplementary PRO tools (e.g. fatigue, headache) versus those who do not. These comparisons will not rely on device removal.
- NiLPT and chromium LPT results (both the continuous measurement as well as the positive / negative assessment) in subjects with Essure and adjudicated hypersensitivity reactions can be compared to NiLPT and chromium LPT results in subjects with Essure without hypersensitivity reactions as well as to NiLPT and chromium LPT results in laparoscopic tubal ligation subjects (with and without adjudicated hypersensitivity reactions). Secondary analyses can also be performed in subjects who report positively to events on the Supplementary PRO tools (e.g. fatigue, headache) versus those who do not. These comparisons will not rely on device removal.
- An individual subject's serum or plasma nickel and titanium levels and NiLPT can be compared to baseline levels in order to assess any change. In addition, in cases of removal, subsequent post-removal levels can also be compared.

Autoimmune diseases

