Additional Endpoints	
 
New exposure to metals including new cosmetic or medical permanent implants and/or piercings and its material, wear eyeglasses
 
Change from baseline to 1 Year in serum or plasma nickel level, titanium level— both categorical and continuous forms, association with adjudicated hypersensitivity/allergic/autoimmune events
 
Change from baseline to 1 Year in serum or plasma nickel level, titanium level association with adjudicated hypersensitivity/allergic/autoimmune events
 
Proportion of women who crossed over to alternate sterilization method (e.g., Essure subjects who attempted laparoscopic tubal sterilization)
 

Essure Insert Placement Procedure a	Type of hysteroscopy procedure, reason for second attempt, facility where procedure was performed, premedication, pregnancy test performed within 24 hours of this procedure, hormonal manipulation to promote atrophic or proliferate endometrium, anesthesia used, type of anesthesia used, placement technique, hysteroscopy possible, retroverted uterus, distention medium used, type of distention medium, duration of procedure, Essure procedure attempted, reason Essure procedure not attempted, experienced

	Endpoint/Variable
	AE during hysteroscopy, placement status (by tube), ostium in the field of vision during placement (by tube), if successful - number of Essure trailing coils, number of inserts used (by tube), device type, reasons for unsuccessful placement (by tube), primary reason for unsuccessful placement (by tube), first line confirmation test to be performed, investigator's rating of ease of use of the Essure device, physician's rating of procedure difficulty, experienced AE during Essure implant procedure, Primary method of contraception used just prior to procedure, Primary method of contraception used until reliance assessment, additional procedures performed in conjunction with the Essure procedure
Transvaginal Ultrasound a	Reason for TVU, facility where TVU performed, uterine position at time of TVU, insert detected (by tube), implant location (by tube), reason for unsatisfactory placement (by tube), TVU results satisfactory to allow the subject to rely on Essure, individual who performed TVU, individual who interpreted TVU, physician's rating of procedure difficulty, experienced AE during TVU

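### Serum nickel at 60 months is required in all subjects by Protocol 9.6.3.1 but appears only as a conditional draw in the 60-month visit list (9.2.2.11)

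*Protocol*

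**What the plan says.** The laboratory section (Protocol 9.6.3.1) fixes the nickel schedule without conditions: "This test will be drawn and run at baseline, at 12 months, and at 60 months in all subjects". It adds unscheduled draws when symptoms develop.

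The 60-month visit list (Protocol 9.2.2.11) carries the metals in one place only. The parent item is "If indicated for potential hypersensitivity reaction / pain AEs / allergy / autoimmune disorder", and beneath it stands "Serum or plasma samples for nickel and titanium levels". The only blood item in that list without a condition is "Serum for inflammatory cytokine panel (see Section 9.6.3.1").

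For titanium, 9.6.3.1 reads: "This test will be drawn and run at baseline and at 1 year in all subjects". Later titanium draws are symptom-driven. Of the additional serum taken at 60 months, the same section says: "This will be sent for a repeat inflammatory cytokine panel". Footnote g to Table 9-1 likewise assigns that sample to cytokines and states that it will not be frozen.

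The SAP names one metal endpoint, among the additional endpoints of Table 2: "Change from baseline to 1 Year in serum or plasma nickel level, titanium level". Separately, the text of SAP 6.4 promises change from baseline for every laboratory parameter at every post-baseline visit.

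**The concern.** A site preparing the 60-month visit is likely to work from the list for that visit. Read alone, that list calls for a nickel sample only when a woman is being evaluated for a possible reaction, pain event, allergy or autoimmune disorder. The presence of a year-5 nickel value would then depend on symptoms, which are close to the outcome against which nickel is to be examined.

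Protocol 9.6.1.1 allows nickel levels in Essure women with adjudicated events to be compared with those in Essure women without such events and with laparoscopic women. It also says that "in cases of removal, subsequent post-removal levels can also be compared". If year-5 values exist only where symptoms prompted them, the comparison women at that time are symptomatic too. Women whose symptoms settled after a removal are the ones most likely to have no value.

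**Working it through.** There is no stated figure to reproduce. The check is a comparison of the current sections.

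**Which draws each source schedules**

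| Source | Nickel | Titanium |
|---|---|---|
| 9.2.2.7, 12-month list | all subjects, plus a separate conditional item | all subjects, plus a separate conditional item |
| 9.2.2.8 to 9.2.2.10, lists for 24, 36 and 48 months | conditional only | conditional only |
| 9.2.2.11, 60-month list | conditional only | conditional only |
| 9.6.3.1, at 60 months | all subjects | no scheduled draw |
| Table 9-1, main blood-sample rows | unreadable in this copy | unreadable in this copy |

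1. *Nickel.* At 60 months, 9.2.2.11 and 9.6.3.1 give different answers for any woman without a qualifying symptom. The 12-month list shows how the protocol writes an all-subjects draw: its own item, separate from the conditional one. The 60-month list has no such item.

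2. *Titanium.* The two sections agree. Neither schedules a draw in all subjects after 1 year.

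3. *Amount of data affected.* Let p be the share of women with a qualifying symptom at 60 months, and f the share of women at sites that follow 9.2.2.11 literally.
   - Expected share of year-5 nickel values lost = f × (1 − p).
   - Share lost among symptom-free women at those sites = 100%, whatever p is.
   - The documents give neither p nor f. As an illustration only, take f = 1. With p = 0.10 the loss is 1 − 0.10 = 90%; with p = 0.40 it is 1 − 0.40 = 60%. The finding does not depend on this range.

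4. *Can the loss be repaired?* Footnote g says the 60-month sample is not frozen, and 9.2.2.11 ends study data collection once that visit is complete. An assay omitted then cannot be recovered from stored 60-month serum.

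5. *Removals.* For a removal after month 12, the 60-month nickel draw in 9.6.3.1 is the only scheduled all-subjects metal sample that can follow it. Protocol 9.6.1.6 expects blood levels at various times before and after removal but fixes no time for them.

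**The case against.** The opposing case is substantial, and most of it limits the consequence rather than removing the conflict.

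- *The cross-reference.* The unconditional cytokine item in 9.2.2.11 points to 9.6.3.1, where a careful reader would find the nickel requirement. This makes uniform omission less likely. But the pointer is attached to cytokines, so it does not tell a site that nickel is also due.
- *Table 9-1.* The part that would hold the all-subjects blood rows cannot be read here and may schedule both metals at 60 months. If so, sites may be doing the right thing already. The two text sections would still disagree on nickel.
- *The SAP.* A reader might infer from Table 2 that 60-month metals would go unanalysed. SAP 6.4 does not support that: its general rule reaches every post-baseline visit, and another row of Table 2 lists nickel and titanium levels with no time limit.
- *The comparisons.* The metal comparisons in 9.6.1.1 are worded as possibilities and are not tied to year 5. The only baseline-to-Year-5 summary named there is for cytokines, whose draw is unconditional. Baseline and 12-month metals are scheduled in everyone, so symptom-free and laparoscopic comparators exist at those times.
- *Titanium.* A reader might infer that titanium is also contradictory, because the Amendment 2 rationale says both metals would be assayed at 60 months. That rationale is a change log and cannot establish an error in current text; the operative sections agree with each other. The same rationale expects late metal changes to reflect other sources of exposure rather than Essure, which lowers the stated value of the year-5 data.

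**Conclusion.** The point holds for nickel. Protocol 9.6.3.1 and 9.2.2.11 conflict on whether a symptom-free woman has nickel measured at 60 months. Where the visit list is followed, year-5 nickel would be available only in women worked up for symptoms. The 60-month change-from-baseline summary would then lack symptom-free comparators in both arms, and the gap could not be filled afterwards.

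Severity is moderate. Metal levels are additional endpoints in a study that both documents call exploratory, and no main endpoint rests on year-5 nickel. The size of the loss depends on how many sites follow the list literally and on the share of women with symptoms; the documents give neither. The conclusion also assumes that the unreadable part of Table 9-1 does not already direct sites otherwise. If it does, the remaining problem is one of inconsistent text.

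Two stronger readings are not supported: that titanium is in contradiction, and that the study's metal comparisons as a whole are lost. Titanium is an open question for the sponsor, and the scheduled draws up to 12 months are intact.

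**What to change.** 1. In Protocol 9.2.2.11, add an unconditional item beside the cytokine draw: for all subjects, serum or plasma nickel level. Keep the conditional item for symptom-driven work-up. This brings the list into line with 9.6.3.1.
2. Check that Table 9-1 shows the same 60-month nickel draw, and correct it if it does not.
3. Ask the sponsor whether titanium at 60 months in all subjects is intended. If so, add it to both 9.2.2.11 and 9.6.3.1; if not, no change is needed in those two sections.
4. Optionally, add change from baseline to 60 months in nickel to SAP Table 2, and titanium if it is to be drawn. This is alignment only, since the general rule in SAP 6.4 already covers the values.

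The cost is protocol wording, site notification, and at most one further tube and assay per subject at a visit where blood is already taken from everyone. For women who have already completed the 60-month visit, the report should state how many have a nickel value and how many of those draws were prompted by symptoms.
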